## 9.2 Analysis plan

This is a single-arm, phase II trial to assess the efficacy of the combination of axitinib and avelumab in patients with recurrent or metastatic adenoid cystic carcinoma (ACC) with disease progression within 6 months prior to study enrollment. The primary endpoint is the overall response rate by RECIST 1.1. The trial will be conducted by Simon's 2-stage design and the response rate will be estimated after the second stage (Simon, 1989).

It is assumed that the new regimen will have a target overall response rate at 6 months of 20%. A response rate of 5% or lower is considered a failure and the new regimen will be rejected under this circumstance. When the probability of accepting a "bad" regimen (i.e. ORR $\leq$ 5%) is 0.05 and the probability of rejecting a "good" regimen (i.e. ORR  $\geq$ 20%) is 0.20, Simon's Optimal design requires to enter 10 patients in the first stage. If no patient responds to the treatment, the trial will be stopped and the regimen will be declared as ineffective. If there are one or more responses, 19 more patients will be entered in the study to reach a total of 29 evaluable patients. To ensure that we have 29 evaluable patients we will enroll a total of 30 patients. By the end of the study, the new regimen will be rejected if response rate at 6 months is less than or equal to 3/29 and will be accepted otherwise. The operating characteristics of the trial are given as follows. When the true response rate is 0.05 the probability of stopping the trial early is 60%. On the other hand, if the true response rate is 0.20, the probability to stop the trial early is 10.7%. The expected sample sizes are 17.6 and 27.0 when the true response rates are 0.05 and 0.20, respectively.

To ensure patient safety, the toxicity monitoring will be carried out from the 7th patient using the stopping boundaries calculated based on the beta-binomial distribution. The target toxicity rate by the end of cycle 1 (4 weeks of treatment) is 30%. Toxicity is defined as: as adverse events in the first 4 weeks that are judged to be attributable to one agent or both in combination. Relevant hematological events are grade 4 anemia, grade 4 neutropenia lasting longer than 7 days, febrile

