## Proprietary of MD Anderson Cancer Center

events, including those not identified by laboratory tests, were any grade 3 or worse toxicity except transient ( $\leq 6$  h) grade 3 flu-like symptoms or fever that could be controlled by medical management, transient ( $\leq 24$  h) grade 3 fatigue, local reaction, or headache that resolved to grade 1 or better, grade 3 or 4 nausea and vomiting controlled by optimum medical therapy within 72 h, grade 3 hypertension controlled by medical therapy, grade 3 diarrhea or grade 3 skin toxicity that resolved to at least grade 1 within 7 days of starting medical management (eg, immunosuppressants), any grade 3 or worse amylase or lipase abnormality not associated with symptoms or clinical manifestations of pancreatitis, and tumor flare phenomenon defined as local pain, irritation, or rash localized at sites of known or suspected tumors; grade 3 or 4 increases in alanine aminotransferase or aspartate aminotransferase concentrations concurrent with grade 2 increase in total bilirubin concentration (liver function); non-hematological grade 3 or worse laboratory abnormality that needs medical intervention or led to hospital admission (excluding single laboratory values out of normal range judged unlikely to be related to trial treatment by the investigator, without clinical correlates, and that resolved to grade  $\leq 1$  within 7 days with adequate medical management); and any event related to the trial treatment preventing completion of at least 75% of doses of axitinib or two infusions of avelumab during the first cycle of combined therapy. The prior probability of toxicity for the regimen is modeled by a beta distribution Beta (0.3, 0.7). The following decision criteria will be applied:

stop if  $\text{Prob}\{\theta_{\text{TOX}} > 0.30 \mid \text{data from the trial}\} > 0.7$

Patients recruited will be monitored continuously according to the following stopping boundaries for toxicity.

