**Table 8 Stopping Boundaries**

# Patients evaluated (inclusive)	# Toxicities (inclusive) are considered too toxic
7	3-7
8-10	4-10
11-13	5-13
14-16	6-16
17-19	7-19
20-22	8-22
23-25	9-25
26-28	10-28
29	11-29
30	Always stop with this many patients

The operating characteristics are summarized in the following table.

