# Proprietary of MD Anderson Cancer Center

The above stopping boundaries and operating characteristics are calculated using MultcLean (v.2.1.0) design software downloaded from <http://biostatistics.mdanderson.org/SoftwareDownload>.

Summary statistics including mean, standard deviation, median, and range for the continuous variables, and frequency tables for categorical variables, will be provided. The response rate will be estimated along with its 95% confidence interval. The distribution of time-to-event endpoints including overall survival, progression free survival and duration of response will be estimated using the method of Kaplan and Meier.

The investigator is responsible for completing an efficacy/safety summary report. The efficacy report will be reviewed by the principal investigator and/or study co-chair. For Toxicity monitoring: This will be performed after the first 7 evaluable patients per cohort, complete 1 cycle of study treatment, and every 3 evaluable patients thereafter.

For Response assessment: After the first 10 patients and after 30 patients complete 6 months post-treatment.

A copy of the cohort summary will be placed in the Investigator's Regulatory Binder.

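### The toxicity rule calls for no halt before 7 evaluable patients, even when a third confirmed toxicity among the first 3 to 6 has already made the stop at 7 certain

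*Combined protocol and SAP*

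**What the plan says.** Section 9.2 sets a target toxicity rate of 30% by the end of the 4-week first cycle. The prior is Beta(0.3, 0.7), and the trial stops when the posterior probability that the rate exceeds 0.30 is above 0.7.

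Three statements govern when the rule is applied:

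- The opening of the toxicity paragraph: "the toxicity monitoring will be carried out from the 7 th patient".
- The sentence before Table 8: "Patients recruited will be monitored continuously according to the following stopping boundaries for toxicity".
- The reporting paragraph after Table 9: "This will be performed after the first 7 evaluable patients per cohort, complete 1 cycle of study treatment, and every 3 evaluable patients thereafter".

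The first row of Table 8 is 7 patients, with 3 to 7 toxicities counted as too toxic. The boundary is 4 for 8 to 10 patients and 5 for 11 to 13. It rises by one per block of three up to 10 for 26 to 28, and is 11 at 29. There is no row below 7, so the word for continuous monitoring gives no action before then. Section 9.2 contains no other trial-level stop or enrolment pause tied to early toxicities.

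**The concern.** The toxicity rule is there to protect patients. Under the plan's own table, 3 toxicities in 7 patients end the trial. If the third is confirmed at patient 3, 4, 5 or 6, nothing observed in the remaining patients up to the seventh can reverse that. A plan followed to the letter would still enter those patients on a regimen that its own criterion already classes as too toxic, and their outcomes could not inform the decision.

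What is at stake is exposure in the earliest part of the trial. No error rate and no efficacy conclusion is affected.

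**Working it through.** **Inputs, all from section 9.2.** Prior Beta(0.3, 0.7); target rate 0.30; posterior threshold 0.7; first boundary 3 of 7 (Table 8); maximum enrolment 30; Table 9 stopping probabilities 0.032, 0.225, 0.584, 0.876 and 0.982 at true rates 0.1 to 0.5.

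**Step 1: reproduce the plan's figures.** With x toxicities in n patients the posterior is Beta(0.3 + x, 0.7 + n − x). Taking the smallest x for which P(rate > 0.30) exceeds 0.7 gives every row of Table 8 from n = 7 to 29. At n = 7 the posterior probability is 0.4257 for x = 2 (continue) and 0.7295 for x = 3 (stop). An exact binomial recursion with looks from n = 7 up to n = 29 gives 0.0318, 0.2253, 0.5841, 0.8758 and 0.9824, which is Table 9. Looks only at 7, 10, …, 28 give the same probabilities.

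**Step 2: is the stop fixed before 7?** If 3 of the first k evaluable patients have a toxicity, with k from 3 to 6, then at least 3 of 7 will. The posterior criterion is also already met: 0.989 at 3/3, 0.953 at 3/4, 0.894 at 3/5 and 0.817 at 3/6. The evaluable patients still to come before the look at 7 number 7 − k, that is 4, 3, 2 or 1. The certainty depends on the boundary being applied at exactly 7, as Table 8 does; 3 of 8 would not stop (0.638).

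**Step 3: how often, and how many patients?** The third toxicity falls at patient k with probability C(k−1, 2) p³ (1−p)^(k−3). At p = 0.3 this is 0.0270, 0.0567, 0.0794 and 0.0926 for k = 3, 4, 5 and 6.

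- Probability that the stop is fixed by patient 6: 0.0270 + 0.0567 + 0.0794 + 0.0926 = 0.2557.
- Average number avoidable: 4 × 0.0270 + 3 × 0.0567 + 2 × 0.0794 + 1 × 0.0926 = 0.53.

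For all five Table 9 rates:

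| True rate | P(stop fixed by patient 6) | Average avoidable, all trials | P(all 4 avoidable) = p³ |
|---|---|---|---|
| 0.1 | 0.016 | 0.03 | 0.001 |
| 0.2 | 0.099 | 0.19 | 0.008 |
| 0.3 | 0.256 | 0.53 | 0.027 |
| 0.4 | 0.456 | 1.02 | 0.064 |
| 0.5 | 0.656 | 1.59 | 0.125 |

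When it does happen, the average is the third column divided by the second: about 2.1, 2.2 and 2.4 patients at rates 0.3, 0.4 and 0.5.

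**Step 4: effect of acting at the third toxicity.** Adding a boundary of 3 at n = 3 to 6 and leaving Table 8 as it is from 7 on gives stopping probabilities of 0.0318, 0.2253, 0.5841, 0.8758 and 0.9824, identical to Step 1. The expected number evaluated changes as follows, compared with a look at every patient from 7:

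| True rate | As planned | Acting at the third toxicity |
|---|---|---|
| 0.1 | 29.30 | 29.27 |
| 0.2 | 25.36 | 25.17 |
| 0.3 | 18.48 | 17.95 |
| 0.4 | 12.22 | 11.21 |
| 0.5 | 8.79 | 7.20 |

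If decisions were taken only at 7 and then every 3 patients, the expected numbers at rates 0.3, 0.4 and 0.5 would be 18.56, 12.34 and 8.89. The avoidable averages would then be 0.61 (18.56 − 17.95), 1.13 (12.34 − 11.21) and 1.69 (8.89 − 7.20).

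**The case against.** Starting a rule at a minimum cohort is a normal design choice, and much of the case for leaving this one alone is sound.

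- **The average is small.** It is 0.03 patients at a rate of 0.1 and 0.19 at 0.2. The only dose-limiting figure for this combination in the documents is 1 of 6 in the dose-finding cohort (section 1.4). At a rate of 1/6 the probability is 0.062 and the average 0.12. Six patients in another tumour type are thin evidence, but they do not point to the high rates. This stands; the gain lies where the regimen is toxic.
- **The timing is assumed.** The averages take each 4-week outcome as known before the next patient enters, and the documents give no accrual rate or stagger. With fast accrual, some of these patients would already be on treatment when the third toxicity is known. Enrolment during the 28-day window, or non-evaluable patients, could instead take the number treated above 4. This stands as a limit on the averages; it does not affect the logic.
- **A count can fall until events are adjudicated.** Section 9.2 makes a toxicity depend on attribution and, for some events, on resolution within a set time. This stands, so the point is confined to confirmed toxicities.
- **Individual protection does not wait for patient 7.** Section 5.4 covers dose holds and discontinuation, and section 7.2.1 covers reporting of serious events. This is true, but neither stops enrolment.

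A reader might also infer that the plan contradicts itself by promising continuous monitoring and then a look every 3 patients. The documents do not compel that. The every-3 sentence sits in a paragraph about the investigator's summary report and can be read as a report schedule. Stopping probabilities are the same on either reading.

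**Conclusion.** The point holds as a gap in the rule before 7 evaluable patients. Once 3 confirmed toxicities have occurred among the first 3 to 6, the plan calls for no halt although its decision is fixed, and 1 to 4 more evaluable patients may be treated to no purpose. At the 30% target rate the probability is 0.256 and the average cost about half a patient; at 50% they are 0.656 and about 1.6 patients. These figures assume independent outcomes at a constant rate, every patient evaluable, and each outcome known before the next entry.

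Three stronger readings are not supported:

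- **Table 8 or Table 9 is wrong.** Both reproduce exactly.
- **Four patients is the typical cost.** It needs a toxicity in each of the first three patients, with probability 0.027 at the target rate.
- **The posterior criterion should apply from patient 1.** That is a different rule. It would also stop at 1/1, 2/2, 2/3 and 2/4, and it raises the early-stop probability at a true rate of 0.3 from 0.584 to 0.678.

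The change is worth making because it removes avoidable exposure at no statistical cost.

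**What to change.** Add to section 9.2 that accrual stops as soon as the number of confirmed toxicities reaches the Table 8 boundary for the current block of evaluable patients: 3 within the first 7 evaluable, 4 within the first 10, 5 within 13, 6 within 16, 7 within 19, 8 within 22, 9 within 25, 10 within 28 and 11 within 29. This applies whether or not the rest of the block has been enrolled or has finished cycle 1. State also that the schedule of 7 and then every 3 patients is for summary reports and does not delay a stop.

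Count evaluable patients, as the monitoring plan does, and not patients treated. The plan itself allows for loss: "To ensure that we have 29 evaluable patients we will enroll a total of 30 patients". Suppose one of the first 7 treated is not evaluable, 2 of the other 6 have a toxicity, and the eighth treated has the third. Table 8 then stops at 3 of 7. A rule counting treated patients would go on, since it would now need 4 within 10, and so would protect less than the present plan. The text should also say how patients are ordered within a block when enrolment overlaps.

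The cost is two or three sentences. Tables 8 and 9 stay as they are. The change concerns enrolment only; care of patients already on treatment remains under the existing sections.

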## Proprietary of MD Anderson Cancer Center

events, including those not identified by laboratory tests, were any grade 3 or worse toxicity except transient ( $\leq 6$  h) grade 3 flu-like symptoms or fever that could be controlled by medical management, transient ( $\leq 24$  h) grade 3 fatigue, local reaction, or headache that resolved to grade 1 or better, grade 3 or 4 nausea and vomiting controlled by optimum medical therapy within 72 h, grade 3 hypertension controlled by medical therapy, grade 3 diarrhea or grade 3 skin toxicity that resolved to at least grade 1 within 7 days of starting medical management (eg, immunosuppressants), any grade 3 or worse amylase or lipase abnormality not associated with symptoms or clinical manifestations of pancreatitis, and tumor flare phenomenon defined as local pain, irritation, or rash localized at sites of known or suspected tumors; grade 3 or 4 increases in alanine aminotransferase or aspartate aminotransferase concentrations concurrent with grade 2 increase in total bilirubin concentration (liver function); non-hematological grade 3 or worse laboratory abnormality that needs medical intervention or led to hospital admission (excluding single laboratory values out of normal range judged unlikely to be related to trial treatment by the investigator, without clinical correlates, and that resolved to grade  $\leq 1$  within 7 days with adequate medical management); and any event related to the trial treatment preventing completion of at least 75% of doses of axitinib or two infusions of avelumab during the first cycle of combined therapy. The prior probability of toxicity for the regimen is modeled by a beta distribution Beta (0.3, 0.7). The following decision criteria will be applied:

stop if  $\text{Prob}\{\theta_{\text{TOX}} > 0.30 \mid \text{data from the trial}\} > 0.7$

Patients recruited will be monitored continuously according to the following stopping boundaries for toxicity.

**Table 8 Stopping Boundaries**

# Patients evaluated (inclusive)	# Toxicities (inclusive) are considered too toxic
7	3-7
8-10	4-10
11-13	5-13
14-16	6-16
17-19	7-19
20-22	8-22
23-25	9-25
26-28	10-28
29	11-29
30	Always stop with this many patients

The operating characteristics are summarized in the following table.

**Table 9 Operating Characteristics**

True Toxicity Rate	Prob (stop the trial early)
0.1	0.032
0.2	0.225
0.3	0.584
0.4	0.876
0.5	0.982

# Proprietary of MD Anderson Cancer Center

The above stopping boundaries and operating characteristics are calculated using MultcLean (v.2.1.0) design software downloaded from <http://biostatistics.mdanderson.org/SoftwareDownload>.

Summary statistics including mean, standard deviation, median, and range for the continuous variables, and frequency tables for categorical variables, will be provided. The response rate will be estimated along with its 95% confidence interval. The distribution of time-to-event endpoints including overall survival, progression free survival and duration of response will be estimated using the method of Kaplan and Meier.

The investigator is responsible for completing an efficacy/safety summary report. The efficacy report will be reviewed by the principal investigator and/or study co-chair. For Toxicity monitoring: This will be performed after the first 7 evaluable patients per cohort, complete 1 cycle of study treatment, and every 3 evaluable patients thereafter.

For Response assessment: After the first 10 patients and after 30 patients complete 6 months post-treatment.

A copy of the cohort summary will be placed in the Investigator's Regulatory Binder.

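### Does the planned 95% confidence interval for the response rate conflict with the one-sided two-stage acceptance rule?

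*Combined protocol and SAP*

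**What the plan says.** Section 9.2 gives the design and, after the toxicity tables, one sentence on estimating the primary endpoint.

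- Design and timing of the estimate: "The trial will be conducted by Simon's 2-stage design and the response rate will be estimated after the second stage (Simon, 1989").
- Null rate: "A response rate of 5% or lower is considered a failure and the new regimen will be rejected under this circumstance". The target rate is 20%. The permitted error rates are 0.05 for accepting a bad regimen and 0.20 for rejecting a good one.
- First stage, 10 patients: "If no patient responds to the treatment, the trial will be stopped and the regimen will be declared as ineffective".
- Second stage: "19 more patients will be entered in the study to reach a total of 29 evaluable patients". The regimen is rejected at 3/29 or fewer and accepted otherwise.
- Estimation: "The response rate will be estimated along with its 95% confidence interval".

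The estimation sentence gives a level but no method, no sidedness and no statement about the interim stop. The accept/reject rule does not refer to the interval.

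**The concern.** The 0.05 error rate is one-sided: it is the chance of accepting a regimen whose true rate is 5% or lower. An ordinary binomial interval at two-sided 95% treats the 29 patients as one fixed sample and puts 2.5% in each tail. At the smallest accepting count, 4/29, the two can point in different directions. The report could then say that the regimen was accepted and print an interval containing the rate that the same section defines as failure.

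Two further points add weight. The early stop at 0/10 changes the sampling distribution, so the raw proportion is not unbiased. And because no method is named, whether the interval includes 5% could depend on a choice made after the data are seen. At stake is how the primary result reads, in a trial that Section 1.1 says could lead to a definitive study.

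**Working it through.** **Inputs (Section 9.2).** n1 = 10, stop at 0; n2 = 19; n = 29, accept at 4 or more; p0 = 0.05; p1 = 0.20.

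**1. The plan's own figures.** Early stopping has probability (1 − p)^10, which is 0.599 at 5% and 0.107 at 20%. Expected size is 10 + 19 × (1 − stopping probability): 10 + 19 × 0.4013 = 17.6 and 10 + 19 × 0.8926 = 27.0. All four agree with the plan.

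P(accept) = Σ over x ≥ 1 of P(X1 = x) × P(X2 ≥ 4 − x):

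- at 5%: 0.3151 × 0.0665 + 0.0746 × 0.2453 + 0.0105 × 0.6226 + 0.0010 = **0.0468**
- at 20%: 0.2684 × 0.7631 + 0.3020 × 0.9171 + 0.2013 × 0.9856 + 0.1209 = **0.801**

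The first figure is also the two-stage p-value at 4/29. The one-stage p-value, P(X ≥ 4 | 29, 0.05), is 0.0548. The difference, 0.0079, is the chance of 0/10 followed by 4 or more of 19, a path that the design cuts off.

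**2. Intervals at 4/29 (13.8%).**

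| Method | Level | Interval | Contains 5%? |
|---|---|---|---|
| Clopper-Pearson | 95% | 3.9% to 31.7% | yes |
| Jeffreys | 95% | 4.8% to 29.5% | yes |
| Agresti-Coull | 95% | 4.9% to 31.2% | yes |
| Wald | 95% | 1.2% to 26.3% | yes |
| Wilson | 95% | 5.5% to 30.6% | no |
| Two-stage exact | 95% | 4.1% to 34.3% | yes |
| Clopper-Pearson | 90% | 4.85% to 28.8% | yes |
| Two-stage exact | 90% | 5.1% to 30.8% | no |

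The two-stage exact lower limit solves P(X1 ≥ 1 and X1 + X2 ≥ 4 | p) = 0.025 (or 0.05 for the 90% interval). Allowing for the two stages while keeping 95% does not remove the overlap. The mismatch of level and sidedness is the main cause. Among the exact intervals, agreement with the rule needs both the 90% level and the two-stage method.

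**3. Where it happens.** At 5/29 Clopper-Pearson gives 5.85% to 35.8% and the two-stage exact 95% interval gives 6.0% to 37.1%. Both exclude 5%, so with either method only a count of 4 is affected. That count has probability 12.0% at a true rate of 20%, which is 0.120/0.801 = 15% of acceptances.

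**4. Does the ordinary exact interval cover under this design?** Coverage is the total probability, over 0/10 and every total reachable at 29, of outcomes whose Clopper-Pearson 95% interval contains p. At true rates of 3, 5, 7.5, 10, 12.5, 15, 20, 25, 30 and 35% the lowest value is 95.8%, at 35%. Restricted to trials that reach stage 2, the lowest is 96.6%, at 3%.

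**5. Bias of the raw proportion.** Over all trials, with early stops counted as 0%, its mean is 18.6% at a true 20% and 7.7% at a true 10%, so it is low by 1.4 and 2.3 points. The plan estimates the rate after stage 2. Among trials that get there:

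- true 20%: 0.1859/0.8926 = 20.8%
- true 10%: 0.0772/0.6513 = 11.8%

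So in the trials that would report it, the raw proportion runs slightly high. The design-unbiased estimate (UMVUE) at 4/29 is Σ C(9, x−1)C(19, 4−x) / Σ C(10, x)C(19, 4−x), x = 1 to 4, = 3276/19875 = 16.5%. It is unbiased only when the early stops are averaged in. Given stage 2 its mean is 22.4% at a true 20% and 15.4% at a true 10%, further from the truth than the raw proportion.

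**The case for a change.** The best case for a change is pre-specification. A count of 4 is not remote: its probability is 17% at a true rate of 15% and 14% at 10%, where it makes up 29% and 49% of acceptances. Section 1.1 cites a 9% response rate for axitinib alone, so true rates in that region are plausible. At 4/29 Wilson excludes 5% while the other standard 95% methods include it, so an analyst choosing afterwards could affect how the headline reads. One sentence naming a two-stage exact 90% interval would bring interval and rule into line at no cost in patients.

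The facts stand: no method is named, and at 4/29 the method matters to the lower limit. They do not make a change necessary. The choice of interval cannot alter acceptance, because the count settles it. Moving from 95% to 90% is a preference; it gives agreement with the rule but a narrower interval than the customary one. Leading with the UMVUE would raise the reported rate in exactly the trials that reach stage 2, which is hard to defend as a correction in a single-arm study.

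**Conclusion.** No change to the plan is needed. The arithmetic behind the concern is right: at 4/29 the rule accepts, and the ordinary exact 95% interval, 3.9% to 31.7%, contains 5%. That is an expected result of setting a two-sided 95% interval beside a one-sided 5% rule, and a two-stage 95% interval does the same. The decision and its error rates (0.0468 and 0.801) do not depend on the interval. The ordinary exact interval keeps at least nominal coverage at the rates checked, and the raw proportion does not understate the response rate on average in trials that reach stage 2.

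What remains is an unnamed method for a descriptive interval. An analyst who uses the exact interval, states that acceptance rests on the Simon rule and, if the count is 4, mentions the two-stage one-sided 95% lower bound of 5.1% would report the result fairly under the present text.

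This assumes that the final count is taken on 29 evaluable patients, as the rule in Section 9.2 is written, and that the futility stop at 0/10 is followed.
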